The proposed observational study will evaluate the relationship between measures of psychopathology, disordered eating, and impulsivity, (each assessed preoperatively and in the early postoperative period) and changes in weight and psychosocial status in the first two years after bariatric surgery. Secondary outcomes of prevalence and control of T2D and hypertension, health services utilization, and adherence to antidiabetes and antihypertensive medication will also be assessed. All participants will complete assessments at baseline (before surgery) and at 6, 12, and 24 months follow-up. Secondary aims will examine psychopathology, disordered eating, impulsivity, as well as weight loss, in relation to changes in eating behavior, physical activity, psychosocial status, and substance use in the first two years after bariatric surgery. The study has one specific aim and two secondary aims. Specific Aim 1: To determine the relationship between psychopathology, disordered eating, and impulsivity assessed preoperatively and changes in body weight over the first two years following bariatric surgery. We will determine which individual measures falling under these constructs are important in predicting the relative success of bariatric surgery. We will also examine the relationship of changes in the individual measures (from baseline to 6-months after surgery) on subsequent weight loss. (The study is powered on this aim.) We predict that individual measures of psychopathology, disordered eating, and impulsivity will predict smaller weight losses two years postoperatively. We also predict that smaller changes in measures of impulsivity, psychopathology, and disordered eating within the first 6 postoperative months will be associated with smaller weight losses at postoperative month 24. Secondary Aim 1: To examine the correlation structure among our individual measures, and subsequently will generate and confirm composite measures for the three constructs. Composite measures of psychopathology, disordered eating, and impulsivity will predict smaller weight losses two years postoperatively. We also will estimate the proportion of variance in weight loss accounted for by each composite measure. We predict that confirmatory factor analysis will confirm that our individual measures represent three constructs of psychopathology, disordered eating, and impulsivity. Higher values of these composite measures will in turn predict smaller weight losses at postoperative month 24. Secondary Aim 2: To assess the relationship between baseline measures of interest and postoperative changes in caloric and macronutrient intake, eating behavior, physical activity, and psychosocial status. We predict that participants with greater psychopathology, disordered eating, and impulsivity will report greater caloric intake, less favorable changes in macronutrient intake and eating behavior, participate in less physical activity and report more symptoms of psychosocial distress.

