however, are not universal and vary between patients and across surgical procedures. It is estimated that 20-30% of patients experience suboptimal weight loss or significant weight regain within the first few postoperative years. Reasons for this are not fully understood, but likely involve both physiological processes and behavioral factors (e.g., difficulty adhering to the dietary and physical activity recommendations made prior to surgery). Extreme Obesity More than one-third of American adults are obese, defined by a body mass index (BMI) of 30 kg/m2.1 Furthermore, 8.3% of women and 4.4% of men are extremely obese, defined by a BMI 40 kg/m2.1 Obesity, and extreme obesity in particular, is associated with major health complications including coronary heart disease, hypertension, type 2 diabetes mellitus, sleep apnea, and osteoarthritis.2-4 Surgical Treatment of Extreme Obesity Bariatric surgery is currently recommended for individuals 18 years and older with a BMI of 40 kg/m2 or those with a BMI of 35 kg/m2 in the presence of significant co-morbidities.5,6 Approximately 200,000 individuals are estimated to undergo bariatric surgery in the United States each year. The most common surgical procedures include the gastric bypass (GB), sleeve gastrectomy (SG), and adjustable gastric banding (AGB).7,8 As of 2013, the GB was the most common procedure in the United States, comprising 56% of all procedures; the SG comprised 36.3%.8 Anecdotal reports suggest that the SG is increasing in popularity while the AGB is now performed infrequently. With all three procedures, patients typically reach their maximum weight loss of 20-35% of body weight 12 months after surgery.3,4,9-16 These weight losses are associated with significant improvements in obesity-related co-morbidities and decreased risk of mortality.3,4,11,17-24 Despite these impressive results, studies have found that approximately 25% of patients who undergo bariatric surgery fail to reach or maintain the expected postoperative weight loss.25-27 Courcolous and colleagues, for example, observed that 23.6% of GB patients regained weight between postoperative year 1 and year 2. Less is known about the typical postoperative weight trajectory of patient who have undergone SG. Recent studies have suggested that weight regain is associated with deterioration of many of the health benefits seen with bariatric surgery.12,28-31 Psychosocial Status and Psychopathology in Candidates for Bariatric Surgery Extreme obesity is associated with a significant psychosocial burden, including impairments in quality of life, body image, sexual behavior and other areas of psychosocial functioning.32 While this distress is believed to contribute to the decision to have bariatric surgery, its impact on postoperative outcomes is less clear. At present, little is known about the physiological and behavioral contributions to success or failure of bariatric surgery.33 Regardless, weight regain after bariatric surgery is frequently attributed to preoperative psychosocial and behavioral factors.27,34-41 More specifically, there has been a great deal of interest in the presence of formal psychopathology in bariatric surgery patients and its potential contribution to postoperative outcomes.42-45 At least six studies have described rates of psychopathology in candidates for bariatric surgery using structured diagnostic instruments.46-51 Lifetime rates of any psychiatric diagnoses ranged from 36.8%-72.6%, higher than those reported in most studies of the general population. Mood disorders were the most frequent diagnoses, seen in 22.0%-54.8% of patients. Substance use disorders (SUDs) were found in up to 35.7% of patients and alcohol abuse or dependence in up to 33.2%. Binge eating disorder (BED), defined as eating an unusually large amount of food within a short period of time coupled with a loss of control over eating, has been diagnosed in 4.6% to 27.1% of patients. Current diagnoses (as compared with lifetime) were less common, reported in 20.9%-55.5% of candidates for surgery. Mood disorders were diagnosed in up to 31.5%. BED ranged from 3.4%-41.9%. Current substance use was seen in less than 2% of patients. (Note. The lower percentages of those with current psychopathology, as opposed to lifetime psychopathology, are expected.) While studies of the psychosocial characteristics of bariatric surgery candidates have been informative, they are not without limitations. Many studies have suffered from methodological concerns, including small sample sizes or lack of an appropriate comparison group. Further, establishing psychiatric diagnoses prior to bariatric surgery is challenging. Perioperative guidelines suggest that patients undergo an evaluation with a mental health professional prior to surgery3 and most third party payers require these evaluations. However, most programs do not use structured clinical interviews to establish diagnoses for clinical purposes.52,53 Several studies have suggested that candidates for bariatric surgery engage in impression management prior to surgery, in which they minimize reports of psychopathology to present themselves to the bariatric team in the most favorable light.54-56 To address this issue, assessment of psychiatric symptoms for research purposes is recommended to occur independently from the required clinical evaluation, as we will do in the proposed study. Nevertheless, studies focusing on the relationship between specific diagnoses and postoperative outcomes may fail to account for other psychological constructs that may be shared across diagnoses. Mood disorders, BED, and SUDs all share the common psychological construct of impulsivity, considered an important aspect of executive functioning. A lack of impulse control may contribute to the excessive weight gain seen in extreme obesity and may impact the results of bariatric surgery. Disinhibition and Impulsivity among Persons with Extreme Obesity Studies have suggested that individuals with obesity, and in particular those with extreme obesity presenting for bariatric surgery, show some deficits in executive functioning. For example, candidates for bariatric surgery have shown deficits in working memory, mental flexibility, motor speed and complex attention.57,58 These deficits could impact comprehension and retention of information presented to patients during the preoperative consultation process and, thus, negatively impact the ability to adhere to the dietary and behavioral changes required for an optimal postoperative outcome.45 At the same time, metabolic dysregulation, such as insulin resistance or hyperglycemeia seen in type 2 diabetes, also is associated with cognitive deficits, suggesting a potential physiological mechanism for the relationship.59-61 Dietary disinhibition, defined as a loss of control over eating, plays a central role in the overconsumption of food and, subsequently, the development of obesity.62.63 Disinhibition is similar to impulsivity, the term more commonly used in the substance use and smoking cessation literatures. Impulsivity is a multi-faceted construct and refers to the absence of the ability to inhibit an automatic behavior (otherwise known as response inhibition)64,65 and the tendency to discount future consequences in favor of more immediate outcomes (known as delay discounting).66,67 Similar to the role of disinhibition in obesity, impulsivity contributes to the development of and relapse with SUDs. Indeed, response inhibition and delay discounting are associated with both SUDs68-70 and obesity.71,72 Both also predict response to treatment for both SUDs73-75 and obesity.76 Chronic overeating and binge eating share several neurobiological and behavioral similarities with SUDs.77,78 In this regard, both may be viewed as behavioral disorders, in which intake (of food, alcohol, and/or drugs) escalates to a rate that is unhealthy and maladaptive. Nevertheless, the specific nature of the relationship between binge eating and substance use remains to be fully elucidated.79 There are similarities between binge eating and addictive disorders, including craving for the desired substance (drug or highly palatable food), a sense of loss of control when using, repeated attempts to control use despite clear adverse consequences, and the dedication of much time in obtaining and using the substance.80-82 Thus, the disinhibition observed with obesity and binge eating, the impulsivity seen with substance use disorders, and the emotional dysregulation associated with mood disorders all likely share commonalities (dashed lines in Figure 1) that may both contribute to the development of extreme obesity and also may be associated with weight loss (solid lines in Figure 1) and changes in psychosocial status after bariatric surgery. Psychosocial Status and Psychopathology after Bariatric Surgery In general, individuals who undergo bariatric surgery report dramatic improvements in psychosocial status and functioning postoperatively.83,84 The vast majority of patients report significant reductions in symptoms of depression and anxiety in the first postoperative year. They also report significant improvements in health and weight-related quality of life. Patients also report improvements in body image, sexual functioning, and relationship satisfaction.85-87 The relationship between preoperative psychopathology and postoperative outcomes is less robust.34,84 Livhits and colleagues reviewed this literature and concluded that the preoperative factors of BMI, BED, and the presence of personality disorders provided the strongest negative associations with postoperative weight loss.42 At least two studies have suggested that preoperative psychopathology, particularly mood and anxiety disorders, is associated with smaller weight postoperative weight losses.88,89 The relationship between BED and postoperative weight loss is unclear; some studies have found a relationship between preoperative BED and postoperative weight loss90.91 while others have not.92-94 Additionally, two studies have suggested that a history of substance abuse is associated with larger weight losses following bariatric surgery.95.96 The interpretation of this counterintuitive finding is that the selfregulation skills that help patients maintain their sobriety also help patients adhere to the demands of the recommended postoperative diet. Disinhibition and Impulsivity following Bariatric Surgery Encouragingly, studies have shown that there are improvements in executive functioning in persons with extreme obesity in the first two years after bariatric surgery.97,98 Postoperatively, patients typically report decreases in disinhibition and hunger, as well as increases in cognitive restraint.99,100 The physical aspects of bariatric surgery typically prevent individuals from eating the objectively large amount of food necessary to meet the diagnostic criteria of BED. However, many individuals continue to report the feeling of loss of control over their eating.44 The self-reported inability to control these impulses postoperatively is associated with smaller weight losses and greater emotional distress in the first few postoperative years.91,99,101,102 There is additional evidence that patients have difficulty with impulse control after surgery. A number of studies have suggested that there is an increased risk of substance abuse following bariatric surgery.101,103,104 King and colleagues,105 in their seminal investigation, found an increased rate of alcohol use disorder in the second postoperative year as compared to the year prior to surgery or in the first postoperative year. Other recent studies also have found increases in alcohol or composite substance abuse (drug, alcohol, or cigarettes) in the first two years after bariatric surgery.106-108 Postoperative substance use has been associated with smaller postoperative weight losses, postoperative nocturnal eating, and subjective hunger.109 Patients at

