
Discounting Task (DDT): participants choose between a smaller reward available immediately (e.g., \$20 today) and a larger reward available after a longer delay (e.g., \$40 in a month). People differ in their degree of delay discounting, the extent to which they forgo larger monetary magnitudes in the future in order to obtain immediate rewards. As in previous work, the immediate reward will be fixed and the magnitude and delay of the larger, later reward will vary from trial to trial. Participants will make 51 choices. The primary outcome will be the subjects discount rate, which will be estimated by fitting a logistic regression that assumes a persons decisions are a stochastic function of the difference in subjective value between the two options.127 Keeping with standard behavioral findings128,129 we will assume that subjective value (SV) is a hyperbolic function of the reward amount (A) and delay (D): SV = A/(1+kD), where k is the participants discount rate. Larger values of k indicate a greater degree of discounting future rewards. A composite measure of impulsivity will be calculated by averaging individual z-scores derived from the SST, Stroop interference score, and k-value. We predict that higher levels of impulsivity indicating poor response inhibition and greater discounting of future rewards (i.e., slower SST, higher Stroop interference score, and higher k-values) will be associated with less weight loss 24 months following bariatric surgery. Psychopathology: Psychopathology measures will be administered via interview or questionnaire at the following time points: baseline and 6, 12, and 24 months after surgery. The tasks are: Structured Clinical Interview for the DSM-5, Research Version (SCID-5-RV)129 is a semistructured interview for making DSM-5 diagnoses for mood, anxiety, eating, substance use, and psychotic disorders. A trained clinician or mental health professional who is familiar with the DSM-5 classification and diagnostic criteria administers the measure, which takes about 2.5 hours. Beck Depression Inventory-II (BDI-II)130: survey used to measure mood. It is the most widelyused measure of depressive symptomatology. Alcohol Use Disorders Identification Test (AUDIT)164: assesses the presence of alcohol use disorders before and after surgery. The Drinker Inventory of Consequences131 is a self-administered 50-item questionnaire designed to measure adverse consequences of alcohol use in five areas: Interpersonal, Physical, Social, Impulsive, and Intrapersonal. Each scale provides a lifetime and past 3-month measure of adverse consequences, and scales can be combined to assess total adverse consequences. The Fagerström Nicotine Tolerance Questionnaire132 is an 8-item, self-report designed to measure physical dependence to nicotine. Urine Drug Screens: collected in temperature sensing cups to ensure valid samples. Urines will be tested for common drugs of abuse (cocaine, opiates, amphetamines, methamphetamine, marijuana). A composite measure of psychopathology will be calculated by averaging individual z-scores derived from the presence/absence of DSM diagnoses, the BDI-II score, and the substance use measures. We predict that higher levels of psychopathology will be associated with less weight loss 24 months following bariatric surgery. Eating Behavior: Eating behavior measures will be administered via interview or questionnaire at the following time points: baseline and 6, 12, and 24 months after surgery. Total administration time is approximately 30 minutes. The tasks are: The Eating Inventory134: 51-item self-report inventory that measures three factors related to eating behavior: 1) cognitive restraint, 2) disinhibition, and 3) hunger. Eating Disorders Examination-Bariatric Surgery Version135: Identical to the widely-used Eating Disorders Examination but also measures eating disturbances specific to bariatric surgery by adding specific questions regarding dumping, plugging, chewing and spitting, and vomiting. (Note. The diagnosis of BED will be established from the SCID interview. The results of the EDE-BSV will be used as a continuous variable in the analyses described below.) Night Eating Questionnaire (NEQ)127: 14-item scale that measures symptoms of night eating and has been used in bariatric populations previously. Yale Food Addictions Scale136: 25-item mixed response scale that is used to identify those who are using high sugar/high fat foods in ways similar to symptoms that are markers of substance use, such as tolerance, withdrawal, and loss of control. A composite measure of disordered eating will be calculated by averaging individual z-scores derived from these measures. We predict that higher levels of disordered eating will be associated with less weight loss 24 months following bariatric surgery. Weight: Weight will be measured with a calibrated digital scale with subjects dressed in light clothing and without shoes. Percent weight loss will be calculated from participants current weight (at each assessment point) as compared to their baseline weight. Participants with higher levels of impulsivity, psychopathology, and disordered eating are predicted to lose less weight at 24 months as compared to those with lower levels. Psychosocial Status: Medical Outcomes Study 36-Item Short Form Survey (SF-36)137: used to measure quality of life Impact of Weight on Quality of Life-Lite (IWOOL-Lite) 138: used to measure quality of life Dietary Intake: ASA-24: public-access, freely available (through the National Cancer Institute), web-based tool to obtain high-quality dietary intake data with minimal bias, making it a preferred tool for studying diet and disease associations.139 These 24-hour food recalls will be conducted at each time point for one weekday and one weekend day. Physical Activity: College Alumnus Survey (commonly known as the Paffenbarger Survey140): calculate self-reported leisure time physical activity kilocaloric expenditure per week. The frame of reference will be the past 6

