
The following documents are currently attached to this item:

There are no documents attached for this item.

Deception

Does your project use deception? No

Analysis Plan

Analysis will be conducted using Stata 13.0 (Stata Corporation, College Station, TX). After the completion of quality assurance procedures, descriptive statistics will be summarized for all patients by predictor group (dichotomized). Data screening: Prior to performing analyses, standard data screening/ cleaning procedures will be applied. These procedures will: screen the data for data-entry errors; check for outliers; assess the extent and pattern of missing data; create all summary scores needed for analysis; and check that appropriate assumptions of normality are met. In all analyses, the assumptions underlying the application of all the statistical methods that are used will be examined, principally through the use of standardized residuals, influence diagnostics, and graphical displays. Image processing will include image quality assessment procedures that examine global and region of interest (ROI) based raw and processed temporal signal-to-noise ratio, absolute and relative motion, and signal spike count. Potential outliers will be identified in the cumulative sample by examining quality assessment measures and flagging for further investigation subjects greater than two standard deviations from the mean on any one measure (i.e., behavioral performance, image distortion and artifact, general linear model fit). The purpose of this evaluation is to determine whether the time series is likely valid, and, if so, it will remain. Otherwise it will be corrected, if feasible, or removed from the analysis. The final sample will be examined in a similar fashion to determine whether any subjects warrant data cleaning or require exclusion from the final statistical analysis. Analysis of repeated measures: Our four-session within-subject design will generate multiple outcome measures that belong to the Gaussian family, and we will therefore use standard repeated-measures analysis of variance (ANOVA). Imaging outcomes (perfusion and BOLD) will be modeled using standard voxel-based image analysis techniques (described below) that incorporate random effects. Other outcomes (weight loss, ratings) will be modeled using a linear mixed-effects models framework, using using Stata 13.0 (Stata Corporation, College Station, TX). We could use a population averaged approach such as generalized estimating equations. However, the mixed model approach will provide the flexibility to allow for different error variances for different sessions if necessary. Voxel-based image analysis has limited flexibility, particularly when adding multiple covariates and interaction. When needed, summary values (e.g., mean rCBF, mean BOLD% signal change) extracted from ROIs will be modeled in STATAs mixed-models framework. These models can be extended to include additional explanatory variables (e.g., weight change, heart rate, respirations, age). Primary Aim 1 We will take a mixed models approach. The main interest in this study is the Group x Time interaction, where Group will be a between-subjects factor and Time will be a categorical within-subjects factor. This can be interpreted as population averages (GEE fitting method). Hypothesis 1: We will fit a 2 (Group: Dichotomized Baseline Measures, Low, High) x 3 (Time: change from baseline to month 6, 12 and 24) mixed-effects model for change in weight. Hypothesis 2: We will fit a 2 (Group: Dichotomized difference scores, 6 Month minus Baseline, Low, High) x 2 (Time: change from baseline to months 12 and 24) mixedeffects model for change in weight. In addition, the mixed effects models will include adjustments for surgical procedure, gender, and time since surgery. We recognize that the change in weight could also be associated with effects of several pertinent patient characteristics. To this end, we will consider additional covariates (e.g. sociodemographic variables, comorbidities, medication use, tobacco use, and initial weight). For both hypotheses, we will explore the continuous version of our predictor variables, where in place of Group, we use the real values of the predictor. This yields a difference of slopes with respect to predictor value across time points. Secondary Aim 1 We will use confirmatory factor analysis to verify our expected natural groupings of individual measures into composite measures. We will specify 3 factors and use Varimax rotation. We will assemble composite scores for each of our constructs by summing the standardized score values. We will then standardize the composite score and outcome (change in weight at 24 months). We will estimate the partial correlations (direct and indirect) among individual measures, composites, and outcome in a path analysis as suggested by Figure 1 to estimate the fraction of variance in outcome accounted for by each of the constructs. Secondary Aim 2 The outcomes will consist of (continuous) changes in behavior from baseline. We will use correlation to examine the relationship of baseline impulsivity measures to changes at 6, 12 and 24 months. The exception is changes in diet composition. In this analysis, we will use multivariate regression methods,

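### Secondary Aim 1 names a confirmatory factor analysis but specifies only three factors with Varimax rotation; the two conflict, and as written the expected grouping has no formal test

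*Combined protocol and SAP*

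**What the plan says.** Under Objectives, Secondary Aim 1 makes a prediction: "We predict that confirmatory factor analysis will confirm that our individual measures represent three constructs of psychopathology, disordered eating, and impulsivity". The Analysis Plan for the same aim gives the method: "We will use confirmatory factor analysis to verify our expected natural groupings of individual measures into composite measures". The next sentence supplies the only settings: "We will specify 3 factors and use Varimax rotation". Standardized scores are then summed into composites, and no condition ties that step to the factor result.

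The expected assignment of measures is on paper, in Study Instruments and again in Procedures. For impulsivity: "A composite measure of impulsivity will be calculated by averaging individual z-scores derived from the SST, Stroop interference score, and k-value". For psychopathology, the composite comes from "averaging individual z-scores derived from the presence/absence of DSM diagnoses, the BDI-II score, and the substance use measures". The disordered-eating composite uses the four eating instruments listed there.

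The Background expects the constructs to overlap: "Mood disorders, BED, and SUDs all share the common psychological construct of impulsivity", and "Disinhibition is similar to impulsivity".

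The text I had (some pages were removed, and Figure 1 is not shown) gives no fit criterion, rival model, loading rule or consequence if three constructs are not supported.

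**The concern.** The method sentence and the settings sentence describe different analyses. In a CFA the analyst fixes in advance which measure loads on which factor, and the data can reject that pattern. Varimax is a rotation of a solution in which every measure may load on every factor. If the settings are followed, three factors are extracted because three were requested, and the reader compares the loading table with the expected list by eye.

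At stake is the predicted statement that the measures represent three constructs. Without a model that can be rejected, or a rule fixed beforehand, the same table could be called confirmed or not after it has been seen. Varimax also holds the factor correlations at zero in this step, although the Background expects overlap.

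**Working it through.** The plan gives no power, fit or sample-size figure for this step, so there is nothing to reproduce.

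**Inputs.** n = 300 completed baseline visits (Accrual). Three impulsivity measures (Procedures). The remaining count is an assumption. Six psychopathology indicators (diagnoses, BDI-II, AUDIT, Drinker Inventory, Fagerström, urine screen) and six eating indicators (three Eating Inventory scales, EDE-BSV, NEQ, Yale scale) make 15. Treating the Eating Inventory as one indicator makes 13. All loadings, factor correlations and reading rules below are assumed, and data are Gaussian unless stated.

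**1. What a rotation can test.** The implied correlation matrix is ΛΛ′ + Ψ. Varimax replaces Λ by ΛT with TT′ = I, so (ΛT)(ΛT)′ = ΛΛ′. The fit is unchanged; in simulation the largest difference was about 2×10⁻¹⁵. The rotation therefore carries no test of a grouping.

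**2. Degrees of freedom**, with p indicators and three factors.

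- Unrestricted: [(p−3)² − (p+3)]/2. For p = 15: (144 − 18)/2 = 63. For p = 13: (100 − 16)/2 = 42.
- CFA with the listed assignment and free factor correlations: p(p+1)/2 − (2p+3). For p = 15: 120 − 33 = 87. For p = 13: 91 − 29 = 62.

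The differences, 24 and 20, are the restrictions that express the grouping hypothesis. A Varimax solution imposes none of them.

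**3. How much the reading rule matters.** Grouping true, 15 indicators, loadings 0.65, 500 replicates per setting (a separate 300-replicate repeat in brackets). Percentage read as confirmed:

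| Factor correlation | Largest loading on the predicted factor | Same, and no other loading of 0.30 or more |
|---|---|---|
| 0 | 100 (100) | 100 (100) |
| 0.5 | 100 (100) | 91 (92) |
| 0.7 | 96 (98) | 11 (12) |

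The rules agree when the factors are uncorrelated and disagree sharply when they overlap strongly.

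**4. What the loadings would and would not reveal.**

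- One measure (disinhibition) moved wholly to impulsivity at 0.65: the largest-loading rule confirms 0% at factor correlations 0, 0.3, 0.5 and 0.7. With disinhibition loading 0.5 on impulsivity and 0.3 on eating, it confirms 1%, 3%, 7.5% and 17%.
- Three measures keep their main loading but cross-load (factor correlations 0.3-0.5): the largest-loading rule confirms 100%. The 87-df CFA test rejects 54-69% at cross-loading 0.2 and 96-99.5% at 0.3, against 6-8% when the grouping is right. The stricter rule confirms 0-44%.
- Psychopathology is really two constructs correlating 0.7 or 0.8: the largest-loading rule confirms 93% and 99.5%. The CFA fit test rejects only 51% and 25%.

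**5. Limits of the CFA.**

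- With 13 indicators, loadings 0.6 and data from one general factor (60 replicates), the imposed three-factor CFA was not rejected in 97%. A fit criterion without rival models is therefore not enough.
- If the impulsivity tasks load 0.4 and the other measures 0.6, Varimax recovers the grouping in 97%, 64% and 26% at correlations 0, 0.5 and 0.7. CFA prefers three factors to two in 96%, 91% and 63%.
- With binary indicators and ordinary maximum likelihood, the true model was rejected in 7-12% against a nominal 5%. A categorical estimator was not simulated.

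**The case against.** The plan does name CFA, and the assignment it would test is listed in Study Instruments and Procedures. The Varimax sentence may be loose wording, or may describe a preliminary look, since Secondary Aim 1 begins by examining the correlation structure. This stands in part. A reader might infer that the plan intends only an exploratory analysis; the documents do not support that, because they contain both instructions. What they show is a conflict. If a true CFA is meant, the Varimax sentence cannot be carried out. If Varimax is run, the grouping is not formally tested. Either way the text needs changing, and a rule for non-confirmation is still missing.

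A reader might also infer that a wrong grouping would pass. For a measure that truly belongs to another construct this is not shown: step 4 finds that even the lenient rule usually exposes it. The risk is limited to cross-loading and split constructs, and for a split construct the CFA fit test is itself weak.

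The two reading rules are assumed, so the spread in step 3 shows only that an unstated rule can matter, not what the investigators would conclude. The indicator count cannot be fixed from the documents, but the argument does not depend on it.

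**Conclusion.** The point holds as a conflict between the named method and its settings, with the confirmatory step left unspecified. If Varimax is run as written, the predicted grouping has no formal test: 63 df against 87 with an assumed 15 indicators, or 42 against 62 with 13. The verdict then rests on an unstated rule. With assumed loadings of 0.65 and a true grouping, two rules agree at 100% with uncorrelated factors but give 96-98% and 11-12% at correlation 0.7.

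A reader might infer that all of Secondary Aim 1 is undermined. It is not. Composite membership is listed in advance, and the composites and their prediction of weight loss go ahead whatever the factor analysis shows. The zero factor correlations apply to the factor step only; overlap can still be examined from the measures and the summed composites. The powered aim uses individual measures. What is affected is the construct-validity statement.

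Two scoring details are minor and not part of this point. The plan says of binge eating disorder (BED): "The diagnosis of BED will be established from the SCID interview". Read literally, that places it with the psychopathology diagnoses. The sign given to cognitive restraint in the eating composite also merits a line of clarification.

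**What to change.** Replace the Varimax sentence with a CFA on baseline data. Assign each measure to its construct as listed in Study Instruments and Procedures, fix cross-loadings at zero, leave factor correlations free, and use an estimator suited to the binary indicators. State the fit criterion, compare with one- and two-factor models, and say what will be reported if three constructs are not supported.

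The alternative is to label the step exploratory and drop the claim of confirmation, preferably with the loading rule stated beforehand.

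The cost is a few lines of the Analysis Plan, with no new data or visits. The downside is that the three-construct model may be rejected, or the comparison with two factors may be inconclusive if the impulsivity tasks load weakly.
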